4.2.2.5. Change at 4 months from baseline in absolute and percentage weight

4.2.2.6. Number of drug discontinuation for any reason

4.2.2.7. Compare adherence measured by adherence surveys on week 4 and Week 16 to the pill counts from week 4 and Week 16.

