**6.2.4.4. Baseline Visit**

- 6.2.4.4.1. If required labs have been performed within 30 days baseline may be performed same day and self-completed HIV Symptom Index (HIV-SI, Appendix 2) survey will be completed, baseline labs will be drawn and patient will be given 30 day supply of study drug.
- 6.2.4.4.2. If baseline is not done same day: vitals will be taken prior to HIV-SI survey being completed. Then updated history and symptom based physical will be performed and baseline labs will be drawn. Patient will be given 30 day supply of study drug; first dose will be taken in office.

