**6.2.4.5. Week 4 Visit**

- 6.2.4.5.1. At 4 week visit, vitals will be taken, pill count will be performed, MAAS and HIV-SI surveys completed. Followed by history, symptom based physical, and laboratory exam. Patient will be given 90-day supply of study drug.

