#### 8.2.2.1. Primary Endpoint

8.2.2.1.1. Percentage of subjects reporting suboptimal adherence, analyzed by intention to treat, from baseline to 16 weeks.

8.2.2.1.1.1. *We hypothesize that a minimum of 85% of subjects taking DRV/COB/FTC/TAF will demonstrate an optimal adherence score from baseline to four-months as measured by the Midland ART Adherence Survey.* Optimal adherence is defined as a Rasch score greater than or equal to 90%. Rasch scores range from 0% (no adherence) to 100% - (perfect adherence).

8.2.2.2. Secondary Endpoints. These are descriptive endpoints so no hypotheses are tested.

8.2.2.2.1. Change at 4 months from baseline in tolerability measured by standardized patient reported outcome questionnaire

8.2.2.2.2. Percentage of subjects with greater than or equal to 90% by pill count

8.2.2.2.3. Proportion of subjects that have HIV-1 RNA  $\geq 50$  copies/mL at baseline and at month 4

8.2.2.2.4. Proportion of subjects with significant changes at 4 months from baseline in serum creatinine, AST or ALT

8.2.2.2.5. Change at 4 months from baseline in absolute and percentage CD4.

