## APPENDIX 1: Midland ART Adherence Survey (MAAS)

**Midland ART Adherence Survey**

Survey # \_\_\_\_\_

Age:  18-35  36-49  50-65  66-99      Ethnicity: \_\_\_\_\_      Gender: \_\_\_\_\_How long on ART?  <1 year       1-5 years       6-10 years       11-15 years       16 or more years

1. Do you sometimes forget to take your HIV medications?	 Yes  No	Current prescribed HIV regimen:
3. Have you ever not taken your meds because you felt worse when you took it?	 Yes  No	 Biktarvy  Genvoya  Julica  Triumeq  Isentress/Isentress HD  Stribild  Dulera  Tivicay  Syntuza  Atripla  Complera  Odefsey  Reyataz or Evotaz  Prezista or Prezcobix
4. When you travel or leave home, do you sometimes forget to bring along your medications?	 Yes  No	 Descovy  Truvada  Epzicom  Edurant  Intelence  Sustiva  Selzentry
5. Did you take your HIV medicine yesterday?	 Yes  No	
6. When you feel like your health is good, do you sometimes stop taking your medicine?	 Yes  No	
7. Do you ever miss doses of your medications because of side effects from them? If so, what side effects?	 Yes  No	

8. How often do you take your HIV medications?

- ALWAYS –never miss a dose
- ALMOST ALWAYS-miss 1-2 times a month
- USUALLY-miss 3- 5 times a month
- SOMETIMES-miss more than 5 times, but take more than 5 times a month
- RARELY-take 3- 5 times a month
- ALMOST NEVER-take 1-2 times a month
- NEVER-do not take the medication

9. How many days in the last week did you not take your HIV medication? \_\_\_\_\_

10. How many days in the last month did you not take your HIV medication? \_\_\_\_\_

11. What is your biggest issue with being able to take your medication: \_\_\_\_\_

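### At Week 16 the survey and the pill count compared in 4.2.2.7 cover different periods, so two exact measures can disagree; only at Week 4 do the periods nearly match

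*Protocol*

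**What the plan says.** **The comparison.** Protocol 4.2.2.7: "Compare adherence measured by adherence surveys on week 4 and Week 16 to the pill counts from week 4 and Week 16". No period is attached to either measure at either visit.

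**The survey (Appendix 1, MAAS).** Three questions are dated. Question 5 asks about yesterday, Question 9 asks "How many days in the last week did you not take your HIV medication", and Question 10 asks "How many days in the last month did you not take your HIV medication". Others have no dated window, such as Question 8, "How often do you take your HIV medications", and Question 7, "Do you ever miss doses of your medications because of side effects from them". After baseline the survey is scheduled at Weeks 4 and 16, and at an early discontinuation visit (Table 6.2.4.1.2).

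**The drug supply.** At baseline (6.2.4.4.2): "Patient will be given 30 day supply of study drug; first dose will be taken in office". At Week 4 (6.2.4.5.1): "Patient will be given 90-day supply of study drug". Section 5.5.1 has subjects bring all study medication to every visit, whereas 6.2.4.7.1 takes the Week 16 count from the bottle handed out at baseline.

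**The related claim.** The Part 2 hypothesis in 8.2.2.1.1.1 is that at least 85% of subjects "will demonstrate an optimal adherence score from baseline to four-months as measured by the Midland ART Adherence Survey", with optimal defined as a Rasch score of 90% or more.

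**The concern.** The survey carries the primary endpoint, and 4.2.2.7 is the protocol's only stated check of it against pill counts. That check is informative only if both measures refer to the same days. If they do not, a gap at Week 16 mixes reporting error with real change in adherence between periods, and the data cannot separate the two. A subject who took doses less well in mid-study and better before the visit would look like a misreporter although both answers were true.

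The same gap affects what the survey can support over four months. The dated questions at the two scheduled visits reach about Weeks 0-4 and 12-16, which leaves the middle of follow-up to the undated questions.

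**Working it through.** The plan gives no figure for this comparison. Its one computed figure, the sample size in 8.8.2 (ln 0.05 / ln 0.90 = 28.4, rounded up to 29 against the stated 30), plays no part here.

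**Inputs**
- Survey window: Question 10, last month, taken as 28 days (30 days as the alternative).
- Expected doses, one tablet daily (5.3.1): Weeks 0-4, 28; Weeks 4-16, 12 × 7 = 84.
- Supply: 30 tablets at baseline, 90 at Week 4.
- Pill-count threshold: 90% (8.2.2.2.2).

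**Step 1. Overlap of the periods**

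| Visit | Days counted | Dated survey window | Counted days outside the window |
|---|---|---|---|
| Week 4 | 28 (Weeks 0-4) | last month | none |
| Week 16, count from the Week 4 supply | 84 (Weeks 4-16) | about Weeks 12-16 | 84 − 28 = 56 (67%); 54 (64%) with a 30-day month |
| Week 16, count from the baseline bottle | 28 (about Weeks 0-4) | about Weeks 12-16 | all 28 |

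Over follow-up, 16 − 4 − 4 = 8 weeks lie outside every dated question at the two scheduled visits.

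**Step 2. Both measures exact, 84-day count against a 28-day month**

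Adherence = (days − missed) / days.

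| Missed in Weeks 4-12 | Missed in Weeks 12-16 | Count | Question 10 month |
|---|---|---|---|
| 12 | 0 | 72/84 = 85.7% | 28/28 = 100% |
| 0 | 4 | 80/84 = 95.2% | 24/28 = 85.7% |
| 8 | 4 | 72/84 = 85.7% | 24/28 = 85.7% |
| 0 | 0 | 100% | 100% |

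The measures part when the miss rate differs between periods and agree when it is the same or zero. The largest possible gap is 66.7 points: all 56 early days missed gives 28/84 = 33.3% against 100%.

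If the baseline bottle is counted, the 12 doses in the first row appear in neither measure. With no misses in Weeks 0-4, both read 100%. Agreement can then be as uninformative as disagreement.

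**Step 3. How often chance alone separates them**

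Assume a constant daily probability p of taking the dose, independent days, exact reporting and a 28-day month. For nested windows the gap has variance p(1 − p)(1/28 − 1/84); for separate 28-day windows it is 2p(1 − p)/28. At a 90% cut-off, 28 days allow 2 misses and 84 days allow 8. Exact binomial sums give:

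| p | SD of gap, 84-day count | Opposite sides of 90% | SD of gap, baseline bottle | Opposite sides of 90% |
|---|---|---|---|---|
| 0.95 | 3.4 points | 15% | 5.8 points | 27% |
| 0.90 | 4.6 points | 31% | 8.0 points | 50% |
| 0.85 | 5.5 points | 18% | 9.5 points | 30% |

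With 30 subjects, the 84-day case gives about 5 to 9 discordant pairs (0.15 × 30 = 4.5; 0.31 × 30 = 9.3) without any reporting error. Two exact measures over the same days would give none. These rates compare two percentages of days; they are not rates for the Rasch classification.

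**The case against.** Several points on the other side are sound.

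- **The 84 days are an inference.** The protocol does not say that the Week 16 count covers the time since Week 4, and 6.2.4.7.1 points to the baseline bottle. This stands. It changes the size of the mismatch but does not remove it: read literally, the periods share no days.
- **The survey's 90% cut-off is on a Rasch score.** A reader might infer from Step 2 that the protocol's survey classification reverses. The documents do not support that. The score converts the MAAS (8.5.1.1), including its undated questions, and a subject who missed doses in mid-study could report it there.
- **The measures need not disagree.** With a constant miss rate or no misses they agree, as Step 2 shows.
- **Weeks 4-12 are not wholly unasked.** Only the dated questions miss them. Question 8 and the questions about what happens ever or sometimes may take them in, but give no defined period to set against a count.
- **The endpoint is descriptive and the protocol only says to compare.** Nothing states that disagreement will be called misreporting. This limits the harm, and labelling Week 16 descriptive would add nothing, since 8.2.2.2 and 8.7.1 already make every secondary endpoint so.
- **Section 8 does not list this comparison.** Its method may be in the statistical analysis plan, so no omission is claimed. The periods are set by the survey wording and the dispensing schedule in the protocol.
- **The hypothesis may mean two visits, not continuous coverage.** The primary endpoint in 4.2.1.1 is a change from baseline to 4 months, so that reading is fair. The wording allows both, which is a reason to state the period.

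**Conclusion.** The point holds in limited form. At Week 4 the survey's last-month question and the pill count cover nearly the same days. At Week 16 they do not on either reading of the protocol: 56 of 84 counted days (54 with a 30-day month) lie outside the dated survey window, or all of them do if the baseline bottle is counted. Exact measures can then differ, by up to 66.7 points in the 84-day case, and the difference is not evidence of misreporting.

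The overlap figures assume visits on schedule and a month of 28 or 30 days. The discordance rates rest also on the assumed daily adherence of 85% to 95% and independent days. The defect is confined to the Week 16 part of one descriptive secondary endpoint and to how far the survey result can be stretched over four months. It does not bear on the sample size.

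**What to change.** 1. **Reconcile 6.2.4.7.1 with 5.5.1 and 6.2.4.5.1**, so that it is clear which supply is counted at Week 16 and that the count includes the drug dispensed at Week 4. The remaining changes depend on this.
2. **In 4.2.2.7, rest the agreement analysis on Week 4.** Compare the percentage of days taken from Question 10 with the pill-count percentage, and show the Rasch score alongside, since it is not a percentage of doses.
3. **Report the Week 16 comparison with both periods stated**, and say that disagreement there is not to be read as reporting error.
4. **Base any statement about the whole four months on the cumulative pill count** from baseline to Week 16: 30 + 90 = 120 tablets dispensed against 28 + 84 = 112 doses expected. In 8.2.2.1.1.1 and 8.6.1.2, describe the Week 16 survey result as adherence reported at Week 16, whose dated questions cover the last month.

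No new visit or instrument is needed, because 5.5.1 already has all study medication brought to each visit; the counting instruction must be settled first. The price is that the agreement conclusion rests on one visit and the survey-based claim is narrower.

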#### 4.2.1. Primary Endpoint:

4.2.1.1. Change in adherence from baseline to 4 months, measured by adherence surveys

#### 4.2.2. Secondary Endpoints:

4.2.2.1. Change at 4 months from baseline in tolerability measured by standardized patient reported outcome questionnaire

4.2.2.2. Proportion of subjects that have HIV-1 RNA  $\geq$  50 copies/mL at baseline and at Week 16

4.2.2.3. Proportion of subjects with significant changes at 4 months from baseline in serum creatinine, AST or ALT

4.2.2.4. Change at 4 months from baseline in absolute and percentage CD4.

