## 8.6. Part 2 –

### 8.6.1. Primary Endpoint

- 8.6.1.1. Percentage of subjects reporting suboptimal adherence, analyzed by intention to treat, from baseline to four-months using Rasch scores. The hypothesis testing will be carried out at the 5% (2-sided) significance level unless otherwise specified. P-values will be rounded to three decimal places. P-values less than 0.001 will be reported as <0.001 in tables. P-values greater than 0.999 will be reported as >0.999.
- 8.6.1.2. We hypothesize that a minimum of 85% of subjects taking DRV/COB/FTC/TAF will demonstrate optimal adherence from baseline to four-months as measured by the Midland ART Adherence Survey. Optimal adherence is defined as a Rasch score greater than or equal to 90%. Rasch scores range from 0% (no adherence) to 100% (perfect adherence).

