## 8.7. Part 2 - Analysis of Secondary End-Points

### 8.7.1. These are descriptive endpoints so no hypotheses are tested.

- 8.7.1.1. Change at 4 months from baseline in tolerability measured by standardized patient reported outcome questionnaire.
- 8.7.1.2. Percentage of subjects with greater than or equal to 90% by pill count
- 8.7.1.3. Proportion of subjects that have HIV-1 RNA  $\geq$  50 copies/mL at baseline and at month 4
- 8.7.1.4. Proportion of subjects with significant changes at 4 months from baseline in serum creatinine, AST or ALT
- 8.7.1.5. Change at 4 months from baseline in absolute and percentage CD4.
- 8.7.1.6. Change at 4 months from baseline in absolute and percentage weight
- 8.7.1.7. Number of drug discontinuation for any reason

8.7.2. All data will be summarized. For baseline characteristics and safety outputs a total overall column will be included to summarize all subjects. Data will be summarized by visit. In summary tables of continuous variables, the arithmetic mean (AM), median, 95% confidence interval (CI), standard deviation (SD) and standard error (SE) will be presented to one more decimal place than the original data. In summary tables of categorical variables, counts and percentages will be used.

8.7.3. We will identify and classify the case mix or heterogeneity of subjects adherence we will use latent class analysis (LCA); which allows us to identify a finite number of latent subgroups and to explore how treatment effect varies across these subgroups. Using the clinical, psychosocial and demographic variables we will classify subjects into latent homogenous classes based on similar response patterns.

8.7.4. Using the latent classes identified above we will use class membership (latent class) in a as a predictor of a distal standardized outcome adherence range from 0 to 100.

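### The Part 2 pill-count secondary endpoint has two definitions, and the survey-versus-pill-count comparison listed in section 4 is not carried into section 8

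*Protocol*

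**What the plan says.** Protocol 4.2.2.7 is a comparison of two adherence measures at two named visits: "Compare adherence measured by adherence surveys on week 4 and Week 16 to the pill counts from week 4 and Week 16".

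Section 8 lists the Part 2 secondary endpoints twice, in 8.2.2.2 and in 8.7.1. In both, the pill-count item reads "Percentage of subjects with greater than or equal to 90% by pill count". It names no visit, no dosing interval and no survey. Section 8.7.1 adds "These are descriptive endpoints so no hypotheses are tested", and 8.7.2 gives a general rule: "Data will be summarized by visit".

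The primary measure is the survey. Section 4.2.1.1 has "Change in adherence from baseline to 4 months, measured by adherence surveys", and 8.6.1.2 sets the cut-off: "Optimal adherence is defined as a Rasch score greater than or equal to 90" percent.

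Both measures are taken at both visits. For Week 4, 6.2.4.5.1 says "At 4 week visit, vitals will be taken, pill count will be performed, MAAS and HIV-SI surveys completed", and 6.2.4.7.1 schedules a pill count and the MAAS again at Week 16. On supply, 6.2.4.4 gives 30 days of drug at baseline and 6.2.4.5.1 gives 90 days at Week 4. Section 6.2.4.7.1 nevertheless takes the Week 16 count from the bottle handed out at baseline.

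**The concern.** The other six Part 2 secondary endpoints pass from section 4 to section 8 in nearly the same terms. Only this one turns into a different quantity. An analyst working from section 8 would report a pill-count percentage and never produce the comparison; one working from section 4 would do the reverse. An analysis plan that followed either section would depart from the other.

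The comparison is the more informative of the two. The primary outcome is self-reported, in a study where every Part 2 subject is switched to the same drug, and the pill count is the other direct measure of doses taken. If only two percentages are reported and they happen to be close, a reader may take them as mutual confirmation, although many subjects could be classed in opposite ways. At Week 16 there is a further difficulty: as the visit text stands, the count does not cover the drug dispensed for the preceding 12 weeks.

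**Working it through.** **1. The two definitions side by side**

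| | 4.2.2.7 | 8.2.2.2.2 and 8.7.1.2 |
|---|---|---|
| Quantity | Survey adherence compared with pill count | Percentage of subjects at or above 90% by pill count |
| Visits | Weeks 4 and 16 | None in the item; by visit under 8.7.2 |
| Survey involved | Yes | No |

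The comparison appears nowhere in section 8, and the 90% percentage appears nowhere in section 4.

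**2. Sample size, used as the denominator below**

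Section 8.8.2 uses n = ln(1 − 0.95)/ln(1 − 0.10) = 28.43, which rounds up to 29. The plan states 30, which is close enough. The point does not depend on this figure; 30 is used as the target enrolment.

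**3. What two percentages say about agreement**

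The protocol gives no expected pill-count result, so the counts here are assumed. Section 8.6.1.2 hypothesises at least 85% optimal: 0.85 × 30 = 25.5, so take 26. Let s be the number optimal by survey, p the number at or above 90% by pill count, and b the number meeting both. Then b lies between max(0, s + p − 30) and min(s, p), and agreement = (b + 30 − s − p + b)/30.

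- s = 26, p = 26: b runs from 22 to 26. At b = 22, agreement = (22 + 0)/30 = 73.3%, with 8 subjects discordant. At b = 26, agreement = (26 + 4)/30 = 100%.
- Chance agreement in both tables = (26/30)² + (4/30)² = 692/900 = 0.769. Kappa is therefore (0.733 − 0.769)/(1 − 0.769) = −0.15 in the first and 1.00 in the second.
- s = 26, p = 21: b runs from 17 to 21, so agreement runs from 17/30 = 56.7% to (21 + 4)/30 = 83.3%.

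Identical percentages are thus compatible with perfect agreement and with agreement no better than chance.

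**4. What the Week 16 count covers**

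Sixteen weeks is 112 days; Week 4 to Week 16 is 84 days. The baseline bottle covers at most 30/112 = 27% of the study period. The 90-day supply from Week 4 would cover the 84 days, but 6.2.4.7.1 does not say that it is counted.

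**5. How much the open Week 16 interval could matter**

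Assume independent daily misses at one common rate, and let X be the number of missed doses in n days. P(at or above 90%) = P(X ≤ 0.1n, rounded down), with X binomial. At a 7% miss rate this is 0.867 over 84 days (8 misses allowed) and 0.907 over 112 days (11 allowed), a gap of 4 points. At 10% it is 0.534 and 0.554, a gap of 2 points. Between these two intervals the effect is small. The larger problem is that a count from the baseline bottle does not measure either interval.

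**The case against.** Several points on the other side are sound.

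- **Timing.** A reader might infer that the section 8 percentage is wholly undated and could move by some 22 points with the period chosen (0.688 over 28 days against 0.907 over 112, at a 7% miss rate). The document does not support that. Section 8.7.2 requires by-visit summaries, and pill counts are scheduled only at Weeks 4 and 16. What stays open is the Week 16 interval. The 22 points are also close to a worst case: at a 10% miss rate the same contrast is 9.5 points (0.459 against 0.554).
- **Delivery.** A reader might infer that the comparison will not be done. That goes too far. The endpoint stands in section 4, the paired data are collected, and the protocol refers to an SAP that is not shown. The supportable statement is that section 8 does not carry the comparison.
- **Purpose.** A reader might call the pill count the planned and only objective check on the primary measure. The protocol states no such purpose, and HIV-1 RNA is measured at the baseline, Week 4 and Week 16 visits. Viral load does not count doses, but it is an objective result that bears on adherence.
- **Meaning of the comparison.** Section 4.2.2.7 does not say that subjects must be classed individually. Two by-visit percentages at a common cut-off of 90 are a possible, weak reading. Even so, section 8 never sets them against each other, and step 3 shows how little they would reveal.
- **Weight.** The endpoint is descriptive, and the ranges in step 3 are arithmetic bounds from assumed counts, not expected results.

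These points limit the finding. They do not remove the conflict between two definitions of one endpoint, which is an inconsistency within the protocol and not a detail left for the SAP.

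**Conclusion.** The point holds in a limited form. Section 4 and section 8 define the pill-count secondary endpoint differently, and the section 4 comparison has no counterpart in section 8. By-visit reporting settles which visits are meant, but neither the comparison nor the Week 16 dosing interval. For illustration, with 26 of 30 subjects optimal on each measure, the section 8 percentages leave agreement anywhere between 73% and 100%; this rests on assumed counts at the target enrolment. Separately, the Week 16 count as described rests on a bottle covering about 27% of the 16 weeks, which does not fit with the 90-day supply at Week 4, so the Week 16 side of the comparison cannot be computed over the study period, or since Week 4, until those sections are reconciled. The primary analysis is not affected. The change is worth making because it is cheap and gives a listed endpoint an analysis.

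**What to change.** 1. Carry the 4.2.2.7 comparison into 8.2.2.2 and 8.7.1 as a descriptive paired 2x2 table at each of Weeks 4 and 16: MAAS class (Rasch score at or above 90%) against pill-count class (at or above 90%), with percent agreement and a 95% CI. Kappa is optional, as it is imprecise at this size: for an assumed table of 24 optimal on both measures, 2 and 2 discordant and 2 on neither, kappa is 0.42 with a bootstrap 95% CI of about −0.10 to 0.84.
2. If the 90% pill-count percentage is kept, list it as its own endpoint in section 4 and report it per visit with a stated denominator.
3. Reconcile 6.2.4.4, 6.2.4.5.1 and 6.2.4.7.1 on which bottles the Week 16 count covers, so that the Week 16 figure can be computed.

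The cost is wording in 4.2.2, 8.2.2.2 and 8.7.1, the pill-count source sentence in 6.2.4.7.1, and one extra table. Items 1 and 2 use measures already scheduled. No extra visits or subjects are needed.
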